6.0 Study Population

Inclusion Criteria

1. Patients with MDS (up to 20% blasts) of any risk. Patients with lower risk MDS (low and int-1 by IPSS) could have received prior non-hypomethylating agent therapy (ie growth factors or lenalidomide). Patients with higher risk MDS (int-2 or high by IPSS) should not have received prior therapy with a hypomethylating agent.
2. Age 18 years or older.
3. Adequate organ function: creatinine ≤ 2.5 x ULN; serum bilirubin ≤ 2.5 x ULN; AST and ALT ≤ 2.5 x ULN.
4. ECOG performance status ≤ 2
5. Females of childbearing potential must have a negative serum or urine beta human chorionic gonadotrophin (β -hCG) pregnancy test result within 24 hours prior to the first dose of treatment and must agree to use an effective

contraception to avoid pregnancy for 23 weeks (30 days plus the time required for nivolumab to undergo five half-lives) after the last dose of investigational drug. Females of non- childbearing potential are those who are postmenopausal greater than 1 year or who have had a bilateral tubal ligation or hysterectomy.

6. Males who have partners of childbearing potential must agree to use an effective contraceptive method during the study and for 31 weeks after the last dose of nivolumab.
7. Patients or their legally authorized representative must provide written informed consent.

Exclusion Criteria

1. History of another primary invasive malignancy that has not been definitively treated or in remission for at least 2 years. Patients with non-melanoma skin cancers or with carcinomas in situ are eligible regardless of the time from diagnosis (including concomitant diagnoses).
2. Any major surgery, radiotherapy, chemotherapy, biologic therapy, immunotherapy, experimental therapy within 2 weeks prior to the first dose of the study drugs.
3. Patients with any other known concurrent severe and/or uncontrolled medical condition (e.g. uncontrolled diabetes; cardiovascular disease including congestive heart failure NYHA Class III or IV, myocardial infarction within 6 months, and poorly controlled hypertension; chronic renal failure; or active uncontrolled infection) which, in the opinion of the investigator could compromise participation in the study.
4. Patients unwilling or unable to comply with the protocol.

5. Patients who are on high dose steroid (ie prednisone or equivalent more than 10 mg a day) or immune suppression medications.

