7.0 Treatment Plan

We plan to study 2 different patient groups (lower risk MDS [defined as low and int-1 by IPSS] and higher risk [defined as int-2 and high risk by IPSS]) with 2 cohorts each. Each cohort will be composed of N=20 patients. Accrual to cohort will be sequential in each patient group. Accrual will be parallel for each patient group.

All treatments can vary +/- 3 days.

1. Lower Risk MDS cohorts (Low and Int-1):

- Cohort 1: Lirilumab single agent Q4 wks.
- Cohort 2: Lirilumab Q4 weeks+ Nivolumab, Q2 wks X 9 cycles then both Q4 wks.

2. Higher Risk MDS cohorts (Int-2 and High):

- Cohort 3: 5-azacitidine IV, D1-7 of 28 day cycle, in combination with Lirilumab IV on D7

- Cohort 4: 5-azacitidine IV, D1-7 of 28 day cycle, in combination with Lirilumab IV Day 7 and Nivolumab IV D7 & D21 X 9 cycles then D7 only on Cycle 10 +

Specific cohorts can be closed based on ongoing experience with this trial or other relevant information.

Patients will receive study drug(s) according to the following treatment plan. Individual minor variations in the initiation of therapy, are acceptable as indicated by patient condition and physician judgment. These variations should be documented in the patient's medical record.

Dosing calculations for Nivolumab and 5-Azacitidine will be based actual body weight.

Single agent:

Lirilumab: Patient will receive lirilumab 3 mg/kg IV over approximately 60 minutes every 4 weeks. One cycle is defined as 4 weeks.

Combination:

Lirilumab and Nivolumab: Patient will receive Nivolumab 3 mg/kg IV over approximately 60 minutes every 2 weeks for 9 cycles. Lirilumab will be administered at 3 mg/kg IV over approximately 60 minutes once every 4 weeks. One cycle will be defined as 4 weeks.

Azacitidine+ lirilumab: Azacitidine 75 mg/m² IV daily x 7 days and lirilumab 3 mg/kg IV over approximately 60 minutes on day 7. A cycle will be considered 4 weeks.

Azacitidine+ lirilumab + Nivolumab: Azacitidine 75 mg/m² IV daily x 7 days followed on day 7 by nivolumab and lirilumab and nivolumab also on day 21. A cycle will be

considered 4 weeks. Doses of nivolumab and lirilumab are 3 mg/kg IV each over approximately 60 minutes.

Dose Adjustments

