Based on the adverse effect profiles of the 3 agents, the following dose adjustments are recommended. Hematological toxicities will be attributed primarily to Azacitidine and preferentially will be dose reduced (Table 1). Specific non-hematological toxicities will be attributed primarily to NIVOLUMAB OR LIRILUMAB. No dose reductions of these two agents are allowed, see below.

Table 1: Dose Adjustments for Grade 3 – 4 Hematological Toxicity

	Azacitidine IV (x 7 days)
Level – 1	50 mg/m ² /day
Level – 2	25 mg/m ² /day

Nivolumab and Lirilumab Dose Modification

Nivolumab/ Lirilumab Dose reductions or dose escalations are not permitted.

Dose Delay Criteria:

Because of the potential for clinically meaningful nivolumab-related AEs requiring early recognition and prompt intervention, management algorithms have been developed for suspected AEs of selected categories.

Dose delay criteria apply for all drug-related adverse events

Nivolumab & Lirilumab administration should be delayed for the following:

- Any Grade \geq 2 non-skin, drug-related AE, with the following exceptions:
 - Grade 2 drug-related fatigue or laboratory abnormalities do not require a treatment delay
 - However, dose delays should occur for the following laboratory

abnormalities:

- G2 Creatinine, or
- G2 ALT, AST or total bilirubin
- Any Grade 3 skin, drug-related AE
- Any Grade 3 drug-related laboratory abnormality, with the following exceptions for lymphopenia, leukopenia, AST, ALT, total bilirubin, or asymptomatic amylase or lipase:
 - Grade 3 lymphopenia or leukopenia does not require dose delay.
 - Grade 3 AST, ALT or total bilirubin requires permanent discontinuation of nivolumab
- Any AE, laboratory abnormality, or intercurrent illness which, in the judgment of the investigator, warrants delaying the dose of study medication.

Criteria to Resume Treatment:

Subjects may resume treatment with study drug when the drug-related AE(s) resolve to Grade ≤ 1 or baseline value, with the following exceptions:

- Subjects may resume treatment in the presence of Grade 2 fatigue
- Subjects who have not experienced a Grade 3 drug-related skin AE may resume treatment in the presence of Grade 2 skin toxicity
- Drug-related pulmonary toxicity, diarrhea, or colitis, must have resolved to baseline before treatment is resumed
- Drug-related endocrinopathies adequately controlled with only physiologic hormone replacement may resume treatment

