If the criteria to resume treatment are met, the subject should restart treatment at the next scheduled timepoint per protocol. However, if the treatment is delayed past the next scheduled timepoint per protocol, the next scheduled timepoint will be delayed until dosing resumes.

If treatment is delayed > 6 weeks, the subject must be permanently discontinued from study therapy, except as specified in discontinuation section.

Management Algorithms:

Immuno-oncology (I-O) agents are associated with AEs that can differ in severity and duration than AEs caused by other therapeutic classes. Nivolumab & Lirilumab are considered immuno-oncology agents in this protocol. Early recognition and management of AEs associated with immuno-oncology agents may mitigate severe toxicity. Management algorithms have been developed to assist investigators in assessing and managing the following groups of AEs:

Gastrointestinal, Renal, Pulmonary, Hepatic, Endocrinopathies, Skin, Neurological.

For subjects expected to require more than 4 weeks of corticosteroids or other immunosuppressants to manage an AE, consider recommendations provided in the algorithms. The guidance provided in these algorithms should not replace the Investigator's medical judgment but should complement it.

Discontinuation Criteria:

Treatment should be permanently discontinued for the following:

- Any Grade 2 drug-related uveitis or eye pain or blurred vision that does not respond to topical therapy and does not improve to Grade 1 severity within the re-treatment period OR requires systemic treatment

- Any Grade 3 non-skin, drug-related adverse event lasting > 7 days, with the following exceptions for drug-related laboratory abnormalities, uveitis, pneumonitis, bronchospasm, diarrhea, colitis, neurologic adverse event, hypersensitivity reactions, and infusion reactions:
 - Grade 3 drug-related uveitis, pneumonitis, bronchospasm, diarrhea, colitis, neurologic adverse event, hypersensitivity reaction, or infusion reaction **of any duration** requires discontinuation

 - Grade 3 drug-related laboratory abnormalities do not require treatment

discontinuation except those noted below:

- Grade 3 drug-related thrombocytopenia > 7 days or associated with bleeding requires discontinuation
- Grade 3 drug-related ALT, AST, or total bilirubin require discontinuation
- Any Grade 4 drug-related adverse event or laboratory abnormality, except for the following events which do not require discontinuation:

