diphenhydramine 50 mg IV with methylprednisolone 100 mg IV (or equivalent), as needed. Subject should be monitored until the investigator is comfortable that the symptoms will not recur. Nivolumab will be permanently discontinued. Institutional guidelines will be followed for the treatment of anaphylaxis. Remain at bedside and monitor subject until recovery from symptoms. In the case of late-occurring hypersensitivity symptoms (e.g. appearance of a localized or generalized pruritus within 1 week after treatment), symptomatic treatment may be given (e.g. oral antihistamine or corticosteroids).

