9.0 Patient Evaluation

Pre-Treatment Evaluation: All pretreatment studies should be obtained within 14 days (± 3 days) of entry into the trial, unless otherwise stated.

1. A complete history and physical, including assessment of baseline adverse events.
2. CBC, platelet count, differential (differential can be omitted if WBC is $\leq 0.5 \times 10^9/L$).
3. Creatinine, total bilirubin, ALT, AST, amylase, lipase, and TSH.
4. Pregnancy test (urine or plasma) in females of childbearing potential should be required within 24 hrs of study enrollment or randomization, then every 6 weeks. After discontinuation from nivolumab these should be repeated at approximately 30 days and approximately 70 days [or more frequently if required by local standard].
5. Bone marrow aspirate during the last 14 days preceding study initiation. Cytogenetics will be obtained prior to therapy in patients known to have cytogenetic abnormalities at the time of diagnosis or relapse (results from prior analysis within 4 weeks can be used for this purpose).
6. Chest x-ray.
7. Pretreatment optional correlative studies. Every effort will be made to collect all samples at all time points for all patients; however, missing collection in

one or more of these time points in occasional patients will not be considered a protocol deviation/violation.

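### Criterion 6 counts men's post-treatment contraception from nivolumab, so read literally Cohort 3 men have no defined period after their last azacitidine dose

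*Combined protocol and SAP*

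**What the plan says.** Three rules in the protocol govern reproductive precautions after treatment, and they use different starting points.

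- **Men (Section 6.0, inclusion criterion 6):** contraception "during the study and for 31 weeks after the last dose of nivolumab".
- **Women (Section 6.0, inclusion criterion 5):** contraception for "23 weeks (30 days plus the time required for nivolumab to undergo five half-lives) after the last dose of investigational drug". The length is built on nivolumab, but the clock runs from the investigational drug in general.
- **Pregnancy tests (Section 9.0):** at entry, then every 6 weeks. "After discontinuation from nivolumab these should be repeated at approximately 30 days and approximately 70 days".

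Section 7.0 defines two cohorts without nivolumab: "Cohort 1: Lirilumab single agent Q4 wks" and "Cohort 3: 5-azacitidine IV, D1-7 of 28 day cycle, in combination with Lirilumab IV on D7".

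On azacitidine, Section 5.0 reports embryotoxicity and impaired reproduction in mice and rats. Section 8.3 warns of possible fetal harm and advises men not to father a child during azacitidine treatment. The pregnancy statement in Section 12.0 deals with a child conceived while the man is on study drugs. Neither passage sets a period after the last dose.

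**The concern.** A time limit counted from an event that cannot happen has no start. In Cohorts 1 and 3 there is no nivolumab dose, so the men's 31 weeks never begins, and the two post-treatment pregnancy tests have no due date.

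The part that matters is Cohort 3. Those men receive a drug for which the protocol documents a reproductive hazard, yet the criterion they must agree to on entry does not say how long after the last dose the precaution lasts. For lirilumab alone (Cohort 1) the documents cite no reproductive hazard, so there the same flaw is only a gap in wording. The point concerns participant and partner safety. It does not touch the sample size, the response or toxicity monitoring, or any planned analysis.

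**Working it through.** This is mainly a comparison of texts. Each rule is set against each regimen in Section 7.0:

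| Cohort | Drugs | Men (criterion 6) | Women (criterion 5) | Tests at about 30 and 70 days (Section 9.0) |
|---|---|---|---|---|
| 1 | lirilumab | no start date | 23 weeks from last drug | no start date |
| 2 | lirilumab, nivolumab | 31 weeks from last nivolumab | 23 weeks from last drug | dated |
| 3 | azacitidine, lirilumab | no start date | 23 weeks from last drug | no start date |
| 4 | azacitidine, lirilumab, nivolumab | 31 weeks from last nivolumab | 23 weeks from last drug | dated |

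**Could another rule fill the Cohort 3 gap for men?** The Section 8.3 advice covers time on azacitidine. The Section 12.0 pregnancy statement covers time on study drugs. The first half of criterion 6 applies during the study in every cohort and may run past the last dose, because Section 12.0 allows participation to outlast dosing, but the protocol does not say when it ends. No available section counts a period for men from the last azacitidine or lirilumab dose.

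**Where do the stated lengths come from?** Women: 23 × 7 = 161 days. Taking off the stated 30 days leaves 131 days for five half-lives, an implied nivolumab half-life of 131 / 5 = 26.2 days. The available text gives no nivolumab half-life, so the 23 weeks cannot be reproduced independently. Men: 31 × 7 = 217 days, with no derivation given. No length is derived anywhere for azacitidine or lirilumab.

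**How many people?** Each cohort has 20 places. The wording gap reaches 20 + 20 = 40 of 80 places (Cohorts 1 and 3), and the azacitidine concern at most 20. The number of men is not given. If Cohort 3 resembled the higher-risk azacitidine trial described in Section 5.0, which was 70% male (an assumption), about 0.70 × 20 = 14 would be men. Fewer would have partners of childbearing potential; the median age in that trial was 69.

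**The case against.** The best reply is that nivolumab is being used as shorthand for study treatment. The general discontinuation list in Section 7.0, which serves all cohorts, ends by referring to continued nivolumab dosing, and criterion 5 joins a nivolumab-based length to the investigational drug. That looks like template wording and not a decision to leave Cohort 3 uncovered. It may well be so, but then the text should say it, since Section 6.0 uses the general terms elsewhere. The opposite reply, that criterion 6 is a nivolumab wash-out and simply does not apply, leaves Cohort 3 men with no stated period.

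A second reply is that azacitidine clears fast: Section 5.0 gives mean half-lives of 0.69 hour (subcutaneous) and 0.36 hour (intravenous), and Section 8.3 about 4 hours for total radioactivity. This stands as a reason not to treat 31 weeks as the right length for azacitidine. It does not show that no period is needed, because Section 5.0 also describes incorporation into DNA and RNA, and genotoxicity.

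A third reply is that the consent form or the brochure may carry the instruction. Neither was available, and other parts of the document were also removed, so this cannot be excluded.

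Two stronger readings are tempting, and the documents do not support them:

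- **That Cohort 3 men lose 217 days of protection, or are worse protected than Cohort 4 men by that amount.** The protocol ties the 31 weeks only to nivolumab. It is not a benchmark for azacitidine.
- **That the clock also starts too early in Cohorts 2 and 4, because nivolumab may be stopped alone.** Section 7.0 says "Grade 3 AST, ALT or total bilirubin requires permanent discontinuation of nivolumab", and Section 8.1.5 says of Grade 3 or 4 infusion reactions "Nivolumab will be permanently discontinued". Both triggers also fall under the Section 7.0 list headed "Treatment should be permanently discontinued for the following", and no section says that the other drugs then continue. On the planned schedule, Cohort 4 nivolumab falls on or after the last azacitidine and lirilumab dose of each completed cycle, and in Cohort 2 both drugs share the 4-week schedule after nine cycles. The duty during the study would in any case cover continued dosing.

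**Conclusion.** The point holds as a literal reading of criterion 6: the post-treatment clock for men has the wrong starting event for Cohorts 1 and 3, and in Cohort 3 this leaves no defined period after a drug with a documented reproductive hazard. It is a faulty anchor in a stated rule, worth correcting on safety grounds, and small in reach: at most 20 men, probably few.

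Confidence is high about the wording. It does not extend to saying that these men receive no post-treatment instruction, because the unseen sources might supply one. The pregnancy-test strand is minor: women's contraception is already counted from the last investigational drug, and without nivolumab the 6-weekly tests have no stated end.

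**What to change.** In inclusion criterion 6, replace *last dose of nivolumab* with *last dose of any study drug*, in line with the anchor in criterion 5. Keep 31 weeks as a default until the sponsor sets a duration for the cohorts without nivolumab.

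As a minor matching edit in Section 9.0, replace *After discontinuation from nivolumab* with *After the last dose of any study drug*, so that the tests at about 30 and 70 days have a date in Cohorts 1 and 3.

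The cost is two changes of phrase, plus the consent form if it repeats them, and a few extra pregnancy tests. The main downside is that the default may ask for longer contraception than azacitidine or lirilumab requires, including from Cohort 1 men, for whom no hazard is cited. A sponsor-set duration would remove that.

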7.0 Treatment Plan

We plan to study 2 different patient groups (lower risk MDS [defined as low and int-1 by IPSS] and higher risk [defined as int-2 and high risk by IPSS]) with 2 cohorts each. Each cohort will be composed of N=20 patients. Accrual to cohort will be sequential in each patient group. Accrual will be parallel for each patient group.

All treatments can vary +/- 3 days.

1. Lower Risk MDS cohorts (Low and Int-1):

- Cohort 1: Lirilumab single agent Q4 wks.
- Cohort 2: Lirilumab Q4 weeks+ Nivolumab, Q2 wks X 9 cycles then both Q4 wks.

2. Higher Risk MDS cohorts (Int-2 and High):

- Cohort 3: 5-azacitidine IV, D1-7 of 28 day cycle, in combination with Lirilumab IV on D7

- Cohort 4: 5-azacitidine IV, D1-7 of 28 day cycle, in combination with Lirilumab IV Day 7 and Nivolumab IV D7 & D21 X 9 cycles then D7 only on Cycle 10 +

Specific cohorts can be closed based on ongoing experience with this trial or other relevant information.

Patients will receive study drug(s) according to the following treatment plan. Individual minor variations in the initiation of therapy, are acceptable as indicated by patient condition and physician judgment. These variations should be documented in the patient's medical record.

Dosing calculations for Nivolumab and 5-Azacitidine will be based actual body weight.

Single agent:

Lirilumab: Patient will receive lirilumab 3 mg/kg IV over approximately 60 minutes every 4 weeks. One cycle is defined as 4 weeks.

Combination:

Lirilumab and Nivolumab: Patient will receive Nivolumab 3 mg/kg IV over approximately 60 minutes every 2 weeks for 9 cycles. Lirilumab will be administered at 3 mg/kg IV over approximately 60 minutes once every 4 weeks. One cycle will be defined as 4 weeks.

Azacitidine+ lirilumab: Azacitidine 75 mg/m² IV daily x 7 days and lirilumab 3 mg/kg IV over approximately 60 minutes on day 7. A cycle will be considered 4 weeks.

Azacitidine+ lirilumab + Nivolumab: Azacitidine 75 mg/m² IV daily x 7 days followed on day 7 by nivolumab and lirilumab and nivolumab also on day 21. A cycle will be

considered 4 weeks. Doses of nivolumab and lirilumab are 3 mg/kg IV each over approximately 60 minutes.

Dose Adjustments

Based on the adverse effect profiles of the 3 agents, the following dose adjustments are recommended. Hematological toxicities will be attributed primarily to Azacitidine and preferentially will be dose reduced (Table 1). Specific non-hematological toxicities will be attributed primarily to NIVOLUMAB OR LIRILUMAB. No dose reductions of these two agents are allowed, see below.

Table 1: Dose Adjustments for Grade 3 – 4 Hematological Toxicity

	Azacitidine IV (x 7 days)
Level – 1	50 mg/m ² /day
Level – 2	25 mg/m ² /day

Nivolumab and Lirilumab Dose Modification

Nivolumab/ Lirilumab Dose reductions or dose escalations are not permitted.

Dose Delay Criteria:

Because of the potential for clinically meaningful nivolumab-related AEs requiring early recognition and prompt intervention, management algorithms have been developed for suspected AEs of selected categories.

Dose delay criteria apply for all drug-related adverse events

Nivolumab & Lirilumab administration should be delayed for the following:

- Any Grade \geq 2 non-skin, drug-related AE, with the following exceptions:
 - Grade 2 drug-related fatigue or laboratory abnormalities do not require a treatment delay
 - However, dose delays should occur for the following laboratory

abnormalities:

- G2 Creatinine, or
- G2 ALT, AST or total bilirubin
- Any Grade 3 skin, drug-related AE
- Any Grade 3 drug-related laboratory abnormality, with the following exceptions for lymphopenia, leukopenia, AST, ALT, total bilirubin, or asymptomatic amylase or lipase:
 - Grade 3 lymphopenia or leukopenia does not require dose delay.
 - Grade 3 AST, ALT or total bilirubin requires permanent discontinuation of nivolumab
- Any AE, laboratory abnormality, or intercurrent illness which, in the judgment of the investigator, warrants delaying the dose of study medication.

Criteria to Resume Treatment:

Subjects may resume treatment with study drug when the drug-related AE(s) resolve to Grade ≤ 1 or baseline value, with the following exceptions:

- Subjects may resume treatment in the presence of Grade 2 fatigue
- Subjects who have not experienced a Grade 3 drug-related skin AE may resume treatment in the presence of Grade 2 skin toxicity
- Drug-related pulmonary toxicity, diarrhea, or colitis, must have resolved to baseline before treatment is resumed
- Drug-related endocrinopathies adequately controlled with only physiologic hormone replacement may resume treatment

If the criteria to resume treatment are met, the subject should restart treatment at the next scheduled timepoint per protocol. However, if the treatment is delayed past the next scheduled timepoint per protocol, the next scheduled timepoint will be delayed until dosing resumes.

If treatment is delayed > 6 weeks, the subject must be permanently discontinued from study therapy, except as specified in discontinuation section.

Management Algorithms:

Immuno-oncology (I-O) agents are associated with AEs that can differ in severity and duration than AEs caused by other therapeutic classes. Nivolumab & Lirilumab are considered immuno-oncology agents in this protocol. Early recognition and management of AEs associated with immuno-oncology agents may mitigate severe toxicity. Management algorithms have been developed to assist investigators in assessing and managing the following groups of AEs:

Gastrointestinal, Renal, Pulmonary, Hepatic, Endocrinopathies, Skin, Neurological.

For subjects expected to require more than 4 weeks of corticosteroids or other immunosuppressants to manage an AE, consider recommendations provided in the algorithms. The guidance provided in these algorithms should not replace the Investigator's medical judgment but should complement it.

Discontinuation Criteria:

Treatment should be permanently discontinued for the following:

- Any Grade 2 drug-related uveitis or eye pain or blurred vision that does not respond to topical therapy and does not improve to Grade 1 severity within the re-treatment period OR requires systemic treatment

- Any Grade 3 non-skin, drug-related adverse event lasting > 7 days, with the following exceptions for drug-related laboratory abnormalities, uveitis, pneumonitis, bronchospasm, diarrhea, colitis, neurologic adverse event, hypersensitivity reactions, and infusion reactions:
 - Grade 3 drug-related uveitis, pneumonitis, bronchospasm, diarrhea, colitis, neurologic adverse event, hypersensitivity reaction, or infusion reaction **of any duration** requires discontinuation

 - Grade 3 drug-related laboratory abnormalities do not require treatment

discontinuation except those noted below:

- Grade 3 drug-related thrombocytopenia > 7 days or associated with bleeding requires discontinuation
- Grade 3 drug-related ALT, AST, or total bilirubin require discontinuation
- Any Grade 4 drug-related adverse event or laboratory abnormality, except for the following events which do not require discontinuation:
 - Isolated Grade 4 amylase or lipase abnormalities that are not associated with symptoms or clinical manifestations of pancreatitis and decrease to < Grade 4 within 1 week of onset.
 - Isolated Grade 4 electrolyte imbalances/abnormalities that are not associated with clinical sequelae and are corrected with supplementation/appropriate management within 72 hours of their onset
- Any dosing interruption lasting > 6 weeks with the following exceptions:
 - Dosing interruptions to allow for prolonged steroid tapers to manage drug-related adverse events are allowed. Prior to re-initiating treatment in a subject with a dosing interruption lasting > 6 weeks, the Investigator must be consulted. Tumor assessments should continue as per protocol even if dosing is interrupted
 - Dosing interruptions > 6 weeks that occur for non-drug-related reasons may be allowed if approved by the Investigator. Prior to re-initiating treatment in a subject with a dosing interruption lasting > 6 weeks, the Investigator must be consulted. Tumor assessments should continue as

per protocol even if dosing is interrupted

- Any adverse event, laboratory abnormality, or intercurrent illness which, in the judgment of the Investigator, presents a substantial clinical risk to the subject with continued nivolumab dosing

Supportive Care

Patients will receive a 5-HT3 antagonist, or any other antiemetics at the discretion of the treating physician, prior to each dose of Azacitidine to prevent nausea and emesis.

Routine supportive measures for leukemia patients such as analgesics, blood transfusions, and antimicrobials are permitted. Prophylactic antimicrobials may be prescribed at the discretion of the treating physician.

Patients aged 50 or older may receive their first course of therapy in the Protected Environment if preferred by the treating physician.

Hematopoietic colony stimulating factors may be used at the discretion of the treating physician to provide optimal patient care.

The administration of other anticancer therapies, other investigational agents, or erythropoetic agents is not permitted.

Hydroxyurea can be used in patients with rapidly proliferative disease at the discretion of the treating physician. That said, concomitant use of hydroxyurea with 5-azacitidine will not be recommended.

Treatment may continue until:

1. Clinically significant progressive disease, or

2. Intercurrent illness that prevents further administration of treatment, or
3. Patient request or
4. General or specific changes in the patient's condition render the patient unacceptable for further treatment in the judgment of the investigator, or
5. Unacceptable toxicity that in the opinion of the investigator makes it unsafe to continue therapy.

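### From cycle 10 the cohort list and the dosing paragraphs in Section 7.0 do not give the same nivolumab schedule for Cohorts 2 and 4

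*Combined protocol and SAP*

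**What the plan says.** Section 7.0 (Treatment Plan) first lists the cohorts.

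- Cohort 2: "Lirilumab Q4 weeks+ Nivolumab, Q2 wks X 9 cycles then both Q4 wks".
- Cohort 4: "Nivolumab IV D7 & D21 X 9 cycles then D7 only on Cycle 10". A plus sign follows, so the reduced frequency applies from cycle 10 onward.

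The section then says "Patients will receive study drug(s) according to the following treatment plan" and, after short remarks on variations and body weight, gives dosing paragraphs by regimen.

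- Lirilumab plus nivolumab (Cohort 2): "Patient will receive Nivolumab 3 mg/kg IV over approximately 60 minutes every 2 weeks for 9 cycles", then "Lirilumab will be administered at 3 mg/kg IV over approximately 60 minutes once every 4 weeks" and "One cycle will be defined as 4 weeks". Lirilumab has no cycle limit. Nivolumab is not mentioned after cycle 9.
- Azacitidine plus lirilumab plus nivolumab (Cohort 4): seven days of azacitidine "followed on day 7 by nivolumab and lirilumab and nivolumab also on day 21", in a 4-week cycle. There is no 9-cycle limit and no change at cycle 10.

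The end of Section 7.0 lists the reasons for stopping treatment (progression, intercurrent illness, patient request, change in condition, toxicity). It sets no maximum number of cycles.

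**The concern.** Someone following the dosing paragraphs alone would treat a patient differently from cycle 10 than someone following the list. The linking sentence introduces the paragraphs, not the list, so a reader could fairly take the paragraphs as the operative text.

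Four things depend on there being one schedule.

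- **Late safety.** Safety is the primary objective (Section 1.0). Section 15.0 gives no time window for the toxicities that count, and everyone who received any dose enters the safety analysis.
- **Long-term outcomes.** Duration of response, PFS and OS would be attributed to a regimen whose later part is not uniquely defined.
- **Dates that run from nivolumab.** Male contraception (Section 6.0) is counted from the last nivolumab dose, and the follow-up pregnancy tests (Section 9.0) from stopping nivolumab.
- **Adherence.** A deviation at cycle 10 cannot be judged without one reference schedule. Restarting after a delay also refers to the next scheduled timepoint under the protocol.

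**Working it through.** The plan states no figure for cumulative nivolumab exposure, so there is nothing to reproduce. The check compares the texts and counts infusions.

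**Inputs (Section 7.0).** A cycle is 4 weeks. Through cycle 9 both texts give two nivolumab infusions per cycle. From cycle 10 the list gives one per cycle in both cohorts. The count assumes no missed doses and reads each paragraph literally and alone: none after cycle 9 in Cohort 2, two per cycle without end in Cohort 4.

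**Formulas, infusions through cycle C.**

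- List, Cohorts 2 and 4: 2 × min(C, 9) + max(0, C − 9)
- Paragraph, Cohort 2: 2 × min(C, 9)
- Paragraph, Cohort 4: 2 × C

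| Through cycle | List (both cohorts) | Paragraph, Cohort 2 | Paragraph, Cohort 4 |
|---|---|---|---|
| 6 | 12 | 12 | 12 |
| 9 | 18 | 18 | 18 |
| 10 | 18 + 1 = 19 | 18 | 20 |
| 12 | 18 + 3 = 21 | 18 | 24 |
| 24 | 18 + 15 = 33 | 18 | 48 |

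**Timing against the response endpoint.** ORR is assessed after 6 cycles (6 × 4 = 24 weeks). The texts part only after cycle 9 (9 × 4 = 36 weeks). The printed stopping boundaries and operating characteristics in Section 15.0 depend only on patient counts, priors and assumed rates. Recomputing three early-stopping probabilities from the printed boundaries at 5, 10 and 15 patients gives 0.1241 (toxicity 0.30, ORR 0.70), 0.7261 (0.50, 0.50) and 0.4316 (0.50, 0.70). All three match Tables 3 and 6, and the schedule does not enter the calculation.

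**Last-dose date.** Take a patient treated through cycle 12.

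- Cohort 2, assuming infusions at the start of the cycle and, when given every 2 weeks, again 2 weeks later: the last infusion under the list falls at week 11 × 4 = 44. Under the literal paragraph it falls at week 8 × 4 + 2 = 34. The dates are 10 weeks apart, and the gap grows by 4 weeks with each further cycle.
- Cohort 4: the last infusion is on day 7 of the final cycle (list) or day 21 (paragraph), 21 − 7 = 14 days apart.

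**Does another section settle it?** The allowance of 3 days either way, and the minor variations permitted at the start of therapy (both Section 7.0), do not cover a missing or extra infusion in every cycle. Section 8.1.3 sets a minimum of 12 days between doses, which both schedules meet. No section ranks the list above the paragraphs or the reverse.

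**Can cycle 10 be reached?** Yes, since there is no maximum duration. Section 5.0 reports a median of 9 azacitidine cycles in a randomized phase III trial in higher-risk MDS. Treatment to about this point is therefore plausible in Cohort 4, but that gives no count for this trial.

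**The case against.** The best defence is that the paragraphs are incomplete, not contradictory. The Cohort 2 paragraph agrees with the list on every 2 weeks for 9 cycles and does not say that nivolumab then stops. The Cohort 4 paragraph can be read as describing one cycle. Read together, the list supplies the cycle 10 rule and every sentence can be obeyed at once.

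This stands in part. For Cohort 2 the paragraph is silent, so a flat contradiction cannot be claimed there. A reader might also infer two independent errors pulling in opposite directions, but that pattern appears only if silence is taken to mean none in one cohort and no limit in the other. For Cohort 4 the defence is weaker: the paragraph describes the regimen with day 21 included and no endpoint, and the list ends day 21 after cycle 9. In neither cohort does the protocol tell the reader to complete one text from the other.

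Three other stronger readings are not supported.

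- The paragraphs do carry the mg/kg doses, but nothing says that they are what is used for ordering.
- It is tempting to count all 40 patients in the two cohorts as affected. That is the enrolment ceiling; patients who stop before cycle 10 are untouched, and cohorts may close early.
- The response analysis might seem compromised. It is not, because the texts agree well past the 6-cycle assessment.

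**Conclusion.** The inconsistency is real and of modest consequence. The texts agree through cycle 9 (18 infusions) and part from cycle 10, most plainly in Cohort 4. Read literally, the difference from the list is one infusion per cycle: 3 by cycle 12 (21 against 18 in Cohort 2, 21 against 24 in Cohort 4) and 15 by cycle 24 (33 against 18, and 33 against 48).

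The number of patients concerned lies between 0 and 20 in each cohort, and the documents do not allow it to be narrowed. Within a cohort, exposure could differ if different staff follow different texts. Whether that would happen is not shown, so it should not be said that PFS and OS will describe a mixed regimen, only that they could. The 6-cycle ORR, the printed stopping boundaries and the operating characteristics are unaffected.

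**What to change.** Reconcile the cohort list and the dosing paragraphs in Section 7.0 so that Cohorts 2 and 4 each have one nivolumab schedule from cycle 10, written the same way in both places. The clinical team decides which schedule stands; this review takes no position on it. If any patient has already passed cycle 9, record the nivolumab infusions actually given, so that late safety, PFS and OS can be reported against actual exposure.

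The cost is a change of protocol wording. Sample size, stopping rules and analyses stay as they are.
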